## **Purpose:**

The purpose of this pilot study is to evaluate if cryoneurolysis will be effective to control pain in patient with wrist and hand contracture. Also, to evaluate if there is any correlation between pain reduction with improvement in ROM and spasticity reduction in participants who are already candidate for DNB and cryoneurolysis. The results will increase our knowledge about cryoneurolysis and if it can be used just for pain control and in patients with fixed contracture.

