## **Objectives:**

1. To evaluate the effect of cryoneurolysis on pain in patients with hand and wrist contracture.
2. To assess any changes in wrist and fingers ROM and spasticity in patients with hand and wrist contracture.
3. To evaluate if there is any correlation between changes in ROM and spasticity with pain
4. To record any changes in pain medication that they receive for pain management.

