## **Hypotheses:**

1. Cryoneurolysis can be used as a pain control tool in patients with wrist and hand contracture.
2. Cryoneurolysis can improve wrist and finger ROM and spasticity in patients with hand and wrist contracture.
3. Pain reduction after cryoneurolysis is independent from the increase in ROM and spasticity reduction.
4. The needs for pain medication will decrease after the procedure.

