### **Statistical Analysis:**

A convenience sample of  $n = 25$  patients will be included in this study. This is consistent with existing volumes of consultations to our clinics. Study recruitment will include all patients with wrist and hand contracture that are considered for cryoneurolysis. The outcome measures that we will use are standard clinical measures, but effect sizes are not readily available from previous studies to formally calculate sample size. Furthermore, our study uses an exploratory prospective cohort design, rather than a parallel group trial design, limiting the rationale for providing a sample size calculation.

To assess for statistical significance, a paired t-test on the difference of proportions, applicable to pre-treatment and post-treatment, will be performed. We will employ repeated measures or linear mixed (multilevel) models of change to analyze within-person trajectories in all key outcomes for the intensive repeated measures data spanning the 4-month study period. Such models derive individual parameter estimates for baseline function and change pursuant to nerve or surgical procedure and will directly index the magnitude in improvement for each outcome with everyone serving as their own control (i.e., with change indexed relative to everyone's own personal baseline). If normal distribution in the outcomes does not stand, McNemar's test and

Spearman correlations will be calculated instead of paired t-test and Pearson's correlation, respectively.

The correlation between range of motion and pain score will be reviewed by Pearson's correlation and or Spearman's rank correlation at single time point. The improvement of range of motion or pain scores during two visits will be compared by two sample t test or Wilcoxon rank sum test.

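### The planned correlation uses ROM and pain levels at one visit and omits spasticity, but the purpose and hypothesis 3 ask how changes relate

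*Protocol*

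**What the plan says.** Three places in the protocol set the question.

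- Purpose: "to evaluate if there is any correlation between pain reduction with improvement in ROM and spasticity reduction".
- Objectives, item 3: "To evaluate if there is any correlation between changes in ROM and spasticity with pain".
- Hypotheses, item 3: "Pain reduction after cryoneurolysis is independent from the increase in ROM and spasticity reduction".

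The last paragraph of Statistical Analysis gives the only association analysis whose variables are named: "The correlation between range of motion and pain score will be reviewed by Pearson's correlation and or Spearman's rank correlation at single time point".

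Three other parts of that section bear on the point.

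- The mixed models: "Such models derive individual parameter estimates for baseline function and change pursuant to nerve or surgical procedure", and these "will directly index the magnitude in improvement for each outcome".
- The fallback for non-normal data: "Spearman correlations will be calculated instead of paired t-test and Pearson's correlation, respectively".
- The closing comparison: "The improvement of range of motion or pain scores during two visits will be compared".

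Methods, item 1, has ROM and MAS measured at each assessment. Item 3 has pain scored on the NRS, or on the CNPI where the patient cannot give a rating. Assessments take place at baseline and at 2 weeks, 1 month and 3 months.

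**The concern.** The question is about changes within patients: do those whose pain falls most also gain most ROM or lose most spasticity? A correlation at one visit compares levels between patients. At baseline it contains no treatment-related change at all. At follow-up it mixes differences that existed before treatment with whatever changed afterwards.

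Hypothesis 3 could therefore seem supported or refuted because of how patients differed on entry. The spasticity half of the question has no stated association analysis, and Statistical Analysis names neither spasticity nor MAS anywhere.

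**Working it through.** The protocol states no power, effect size or correlation, so there is no figure of its own to reproduce. The finding rests on comparing the texts. The arithmetic only shows how far the two quantities can differ.

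**1. Question against analysis**

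| | Pain | ROM | Spasticity |
|---|---|---|---|
| Purpose | reduction | improvement | reduction |
| Objective 3 | pain (change not stated) | change | change |
| Hypothesis 3 | reduction | increase | reduction |
| Planned correlation | score, one visit | value, one visit | absent |

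Objective 3 does not attach change to pain, but it does attach it to ROM and spasticity, and one visit cannot supply a change in either.

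**2. Does other text fill the gap?**

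- The mixed models give person-level change, but outcome by outcome. No sentence links the estimates for pain to those for ROM or MAS.
- The Pearson/Spearman fallback names no variables.
- The two-visit comparison concerns ROM or pain, not one against the other. It also shows that the section speaks of improvement when it means change, so the score in the correlation sentence is most naturally read as a level.

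**3. Levels against changes (all inputs assumed)**

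Take baseline variance 1 for ROM and for pain, change variance v, and each change correlated c with its own baseline. Write change = c√v × baseline + e, with a = (1 + c√v)² and b = v(1 − c²). Then:

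- follow-up r = (a·r_base + b·r_e)/(a + b)
- change r = c²·r_base + (1 − c²)·r_e

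Fix follow-up r at -0.30 and let r_base be 0 or -0.6. Example with c = 0, v = 0.5: a = 1, b = 0.5, so -0.30 × 1.5 = -0.45 = r_base + 0.5·r_e. With r_base = 0, r_e = -0.90. With r_base = -0.6, r_e = (-0.45 + 0.60)/0.5 = +0.30. Because c = 0, change r equals r_e.

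Each cell gives change r at r_base = 0, then at r_base = -0.6:

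| c | v = 0.5 | v = 1 | v = 2 |
|---|---|---|---|
| 0 | -0.90, +0.30 | -0.60, 0.00 | -0.45, -0.15 |
| -0.3 | -0.65, +0.05 | -0.42, -0.18 | -0.32, -0.28 |
| -0.5 | -0.48, -0.12 | -0.30, -0.30 | -0.24, -0.36 |

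A second model agrees. With equal variances, the same cross-sectional correlation x at both visits, cross-lag correlation l and within-variable correlation ρ, change r = (x − l)/(1 − ρ). With ρ = 0.5 and x = -0.4:

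- l = -0.4 gives 0
- l = -0.2 gives -0.2/0.5 = -0.4
- l = 0 gives -0.4/0.5 = -0.8

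**4. Precision of the corrected analysis**

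The approximate 95% half-width for Spearman's r at zero is tanh(1.96·√(1.06/(n − 3))). The sample of 25 is the protocol's; the NRS/CNPI split is not given, so smaller n are shown as a range.

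| n on one pain scale | Half-width |
|---|---|
| 25 | ±0.41 |
| 20 | ±0.45 |
| 15 | ±0.52 |
| 10 | ±0.64 |
| 5 | ±0.89 |

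MAS is ordinal and entry requires a MAS of at least 3 (Inclusion criteria, item 3), so tied changes are likely. In a simulation with n = 25, MAS change in four categories with assumed shares of 50/35/10/5% and a latent correlation of -0.6, mean Spearman r was -0.51 with ties and -0.56 without.

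**The case against.** The mismatch between one visit and change is hard to dispute; the best counter-arguments concern its weight.

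- *Spasticity is an omission rather than a misstatement, and an unseen SAP could add it.* Partly right. The mixed models may well cover MAS, and the single-visit restriction is the stronger half. But the protocol does not stay silent on association: it specifies one, without spasticity. An SAP that followed it would keep the gap.
- *The correlation sentence is not labelled as the analysis for objective 3.* True. What can be shown is that no stated analysis relates the changes, and that is enough.
- *The numerical gap may be small.* Also true. With c of -0.3 or -0.5 and v of 1 or 2, the change correlation stays between -0.42 and -0.18 against a single-visit -0.30, which is small beside a sampling error of ±0.41. The entry criteria restrict baseline severity, so such values cannot be excluded. But the planned analysis does not reveal which case applies.
- *In 25 patients the corrected analysis will decide little.* This stands as a limit on what can be concluded. It does not defend the present text, since a single-visit correlation in the same patients is about as imprecise and answers a different question.
- *Assessments are timed from enrolment rather than from the procedure, so change from baseline inherits that.* Correct, but a separate matter.

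**Conclusion.** The concern holds and should be fixed. The stated correlation does not address the purpose or hypothesis 3, nor objective 3 even on its looser wording, and the spasticity half has no stated association analysis. This follows from the protocol's text and does not depend on the illustrative figures, whose inputs are assumed and whose results run from a large discrepancy to none.

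The consequence is confined to one of four objectives and its hypothesis in a pilot study; objective 1 is untouched. Hypothesis 3 claims independence, and with an interval of ±0.41 or wider no analysis of this sample can establish that. The correction makes the analysis match the question but does not make the hypothesis provable.

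**What to change.** Replace the single-visit sentence with wording such as:

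> Change from baseline in pain will be correlated, by a rank-based method, with change from baseline in ROM and, separately, with change in MAS. The visit, ROM measure and MAS muscle group will be named in advance, here or in the SAP. Correlations will be computed within each pain scale (NRS, CNPI) and reported with 95% confidence intervals.

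An acceptable alternative keeps the mixed models and all four visits: add a clause saying that individual change estimates for pain will be correlated with those for ROM and for MAS. On that route, still delete the single-visit sentence, keep the two pain scales separate, and commit to a mixed model, since the section now also allows other repeated-measures methods that may not yield individual estimates. Those estimates are shrunken, so their correlation is approximate.

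The cost is a sentence or a clause. No measurement, visit or patient is added. The drawbacks are wide intervals, wider still within each pain scale, and ties in MAS change that pull a rank correlation towards zero. Hypothesis 3 may stay as worded, provided a small or non-significant correlation is not reported as proof of independence.

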## **Research Design:**

This project constitutes a single-centre, prospective cohort study. Data collection will occur at the Victoria General Hospital (VGH) spasticity clinic. Patients with severe spasticity and contracture are referred to this clinic for different procedures including cryoneurolysis. This study will not interfere or change the patients' medical care. We will do the assessments for the patients who are already candidates for this procedure as a

Effect of the cryoneurolysis on pain and positioning in patients with wrist and hand contracture. 4

Protocol: [H22-03181]

Version 1.1

Jan 9,2023

part of their treatment, besides other provided medical cares and have been accepted to receive it.

All measurements are a part of routine assessment for patients with severe spasticity and contracture.

The evaluation will be done for them after receiving oral and written consent.

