### **Methods:**

The assessment will be done at baseline, 2 weeks, 1 month and 3 months after being enrolled in the study in the same day of their appointments with [name] and includes;

1. Passive and any active range of motions (ROM) of wrist, second and fifth MCP and PIP joints and thumb palmar and radial abduction will be measured by goniometer. Spasticity will be measured based on Modified Ashworth Scale (MAS).
2. The maximum distance between the pulp of the most flexed finger and thumb and the palm of the hand will be measured in centimeter. This distance will be measured during maximal passive extension of the fingers and thumb while the assessor keep the wrist in neutral (or as close to neutral as possible )position.
3. Intensity of pain in the wrist and hand area will be measured by NRS (numerical rating scale), for patients with sufficient cognitive capacity. In this test patients will be asked to score their pain on scale of 0 to 10. Patients who cognitively are not able to score their pain will be assessed by CNPI scale (Checklist of Nonverbal Pain Indicators). In this scale the patient will be observed at rest and during any movement and any nonverbal vocal complaints, facial grimaces, bracing, restlessness, rubbing of the affected area and verbal vocal complaints will be scored accordingly. PI will decide which one of these 2 methods is applicable, based on their assessments, patients' record and in consult with their caregivers.
4. Goal Attainment Scale (GAS): This is a patient-oriented scale to deliver the patient their desired outcomes. Up to 3 individualized, SMART (specific, measurable, achievable, realistic and timed ) goals will be negotiated between participants, caregivers and their physician. At the final visit, they will be asked if they are satisfied with each of these goals and the response will be scored accordingly.

Effect of the cryoneurolysis on pain and positioning in patients with wrist and hand contracture. 5

Protocol: [H22-03181]

Version 1.1

Jan 9,2023

5. Hand hygiene: the evaluator will assess the patients' hands to determine the extent of palm maceration, ulceration or infection; cleanliness of the palm, ease of cleaning and nail trimming; and the effect of hygiene-related disability on other areas of functioning. This assessment is a part of disability assessment scale (DAS). The score ranges from 0 to 3 based on the severity of the maintaining the hand hygiene.

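### The plan compares two visits of a single cohort with tests for independent samples (two-sample t, Wilcoxon rank-sum)

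*Protocol*

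**What the plan says.** The protocol's Research Design section describes the study in these terms: "This project constitutes a single-centre, prospective cohort study". The Methods section sets four assessments of each patient: "The assessment will be done at baseline, 2 weeks, 1 month and 3 months after being enrolled in the study". The Statistical Analysis section gives the design as a reason for having no sample size calculation: "our study uses an exploratory prospective cohort design, rather than a parallel group trial design". The sample is a convenience sample of 25.

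That section names three kinds of test of change:

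- For pre- versus post-treatment, "a paired t-test on the difference of proportions, applicable to pre-treatment and post-treatment, will be performed", with McNemar's test as the fallback if normality fails.
- For the main outcomes over time, repeated-measures or linear mixed models, "with everyone serving as their own control".
- In its last sentence, the "improvement of range of motion or pain scores during two visits will be compared by two sample t test or Wilcoxon rank sum test".

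Nothing says which of these governs when they cover the same outcome.

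**The concern.** The two-sample t-test and the rank-sum test both treat the two sets of values as coming from different, unrelated people. Here they come from the same hands at different visits. Applied to such data, the tests ignore the within-patient correlation and compute the wrong standard error. The sentence also contradicts the within-person approach set out earlier in the same section.

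Pain and range of motion are the outcomes of Objectives 1 and 2; the first is "To evaluate the effect of cryoneurolysis on pain in patients with hand and wrist contracture". With positive within-patient correlation, the likely consequence is that a real improvement is reported as non-significant, with an interval that is too wide, in a study of only 25 patients.

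The rank-sum test matters more than it may seem, because it is the only rank-based test of change that the plan names. The other fallback, McNemar's test, is for binary data. An analyst with skewed 0-to-10 pain scores who follows the text is therefore led to the wrong test.

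**Working it through.** **Readings of the sentence.** It can mean either of two comparisons:

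1. Scores at one visit against scores at another. The same patients supply both sets.
2. Improvement up to one visit against improvement up to another. The same patients again supply both sets, and the two changes share a baseline.

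Independence fails under both.

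**Inputs.** From the protocol: n = 25, one cohort, four visits. The protocol states no power, alpha, effect size or SD, so it has no figure to reproduce. Assumed for illustration: normal data, equal SDs, two-sided alpha 0.05, all 25 patients seen at both visits, between-visit correlation r, and a true change of 0.6 SD.

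**Standard error, reading 1.** In SD units, the two-sample test uses sqrt(2/n). The true standard error of the mean change is sqrt(2(1 − r)/n). The ratio is 1/sqrt(1 − r):

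- r = 0.3: 1/sqrt(0.7) = 1.20
- r = 0.5: 1/sqrt(0.5) = 1.41
- r = 0.7: 1/sqrt(0.3) = 1.83

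**Error rates and power, reading 1.** Simulated bivariate normal pairs, n = 25; 200,000 data sets for the t-tests and 50,000 for the rank tests:

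| | r = 0.3 | r = 0.5 | r = 0.7 |
|---|---|---|---|
| Type I error, two-sample t | 2.1% | 0.7% | 0.1% |
| Type I error, rank-sum | 2.0% | 0.8% | 0.1% |
| Type I error, paired t | 5.1% | 5.0% | 5.0% |
| Power at 0.6 SD, two-sample t | 56% | 57% | 58% |
| Power at 0.6 SD, paired t | 68% | 82% | 96% |
| Power at 0.6 SD, rank-sum | 52% | 53% | 54% |
| Power at 0.6 SD, signed-rank | 66% | 80% | 95% |

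The exact noncentral-t calculation for the paired t-test gives 0.682, 0.821 and 0.960, in agreement with the table.

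**Sensitivity to the assumed effect.** A separate simulation with a 0.5 SD change gave 40%, 38% and 35% for the two-sample t-test, against 53%, 67% and 87% for the paired t-test. Unpaired power falls with r at 0.5 SD but rises at 0.6 SD. This is because the two-sample test needs an observed difference of about 0.57 SD to reach significance, and the two assumed effects lie on either side of it.

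**Interval width.** With an assumed SD of 2 points on the pain scale, the mean 95% interval from the two-sample t-test is 2.26 points wide at every r. The paired interval is 1.93, 1.63 and 1.27 points wide at r = 0.3, 0.5 and 0.7.

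**Standard error, reading 2.** Assume unit variance and the same correlation r between all visits. Each change from baseline has variance 2(1 − r). Two changes sharing a baseline have covariance 1 − r − r + r = 1 − r. Their correlation is (1 − r)/(2(1 − r)) = 0.5 whatever r is. The standard error is therefore 1/sqrt(0.5) = 1.41 times too large, and the type I error is about 0.7%.

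**The case against.** **A between-group reading.** The sentence might mean that change between two visits is the outcome, compared between groups of patients such as responders and non-responders. A two-sample test could then be legitimate. But the protocol defines no such groups, and the sentence speaks of two visits. This reading has no support in the text.

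**A valid analysis is already planned.** The mixed model covers the main outcomes within person, and a paired t-test is named, so Objectives 1 and 2 do not rest on this sentence alone. This stands, and it limits the harm. It does not settle which analysis governs. The paired t-test is also described as a test of proportions, which does not fit pain scores or joint angles.

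**The error is conservative and the study exploratory.** Both are true. No false claim of benefit follows from positive correlation, and no powered hypothesis is at risk. Even so, estimates and their intervals are the main product of a pilot study.

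**The size depends on assumptions.** This also stands:

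- At r = 0, power at 0.6 SD is 55% unpaired and 53% paired, with both type I errors about 5%. At r = 0.1 it is 55% and 57%.
- Entry requires severe baseline values, which could narrow the baseline spread and lower r. If the baseline SD were half the follow-up SD (an assumption), the standard error ratio becomes sqrt(1.25/(1.25 − r)), which is 1.15, 1.29 and 1.51 at r = 0.3, 0.5 and 0.7.
- The Methods section assigns patients who cannot score their pain to an observational checklist. Fewer than 25 may therefore have numerical pain scores, and the interval widths above, in pain-scale points, are illustrative only.

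These points change the size of the loss, not the fact that the named tests do not fit the design.

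**Conclusion.** The concern holds. The protocol names independent-samples tests for data from one cohort measured repeatedly, and it contradicts the within-person approach in the same section. This is a wrong statement, not a detail left to a statistical analysis plan.

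For correlations between 0.3 and 0.7, and under the stated assumptions, the standard error is overstated by 20% to 83%. The nominal 5% test runs at between about 2% and 0.1%. At a 0.6 SD change, the two-sample t-test loses about 12 to 38 percentage points of power against the paired t-test (68 − 56 and 96 − 58). The loss disappears as the correlation approaches zero; repeated measurements on the same hand make a positive correlation plausible.

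It should be fixed. It is not critical, because the error is conservative and the planned mixed model gives a valid alternative.

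**What to change.** Delete the two-sample t-test and the rank-sum test from the last sentence of the Statistical Analysis section. Replace them in one of two ways:

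- Change in range of motion and pain between two visits will be tested by paired t-test or Wilcoxon signed-rank test.
- Contrasts between visits will be taken from the planned linear mixed model, with visit as a categorical factor and a random effect for patient.

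State which analysis governs for each outcome. The mixed model has the advantage of keeping patients who miss a visit, whereas a paired test uses only those seen at both.

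The cost is one sentence of statistical wording, with no new data, visits or patients. The references to proportions and McNemar's test earlier in the section are a separate matter that this change does not resolve; they should be corrected in the same revision.

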**Inclusion criteria:**

1. Adult patients(at least 18 years old).
2. Severe claw hand with less than 4 cm distance between the pulp of the fingers and palm of the hand.
3. MAS $\geq$  3 in wrist and hand muscles interfering with function or causing a clinical problem, due to any neurological condition.
4. Have refractory pain in wrist and hand area with no response to the usual pain management methods including oral medication or botulinum toxin injection.
5. Patients are already candidate for cryoneurolysis for pain and spasticity in their hand and wrist, based on their response to DNB.
6. Ability to attend testing sessions, comply with testing protocols and provide written informed consent. For patients who physically are not able to complete the consent process, a witness may be asked to sign and confirm their willing for participation. Legal representative may be asked to help with consent process for participants who cognitively are not able to consent on their behalf.

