6. A review of analgesics required from patient or caregiver.
7. We will record a video while we are doing the clinical assessment. These videos will be used by [name] for training purposes. During the recording the face will be excluded with a barrier. Any other recognizable marks such as any tattoos will be blurred to maintain the privacy and security of the patients . All patients would have already had this done with their nerve blocks before the procedure. We will remind all patients not to say their names or anything that might identify them to maintain the privacy.

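### Finger-palm distance and MAS both select patients and measure change, and the protocol does not keep the qualifying reading apart from the single baseline

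*Protocol*

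**What the plan says.** **Entry (Protocol, Inclusion criteria).** Criterion 2 is "Severe claw hand with less than 4 cm distance between the pulp of the fingers and palm of the hand". Criterion 3 requires MAS of 3 or more "in wrist and hand muscles interfering with function or causing a clinical problem, due to any neurological condition". Criterion 4 concerns pain but sets no score: "Have refractory pain in wrist and hand area with no response to the usual pain management methods including oral medication or botulinum toxin injection".

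**Outcomes (Protocol, Methods).** Item 2 states: "The maximum distance between the pulp of the most flexed finger and thumb and the palm of the hand will be measured in centimeter". Item 1 includes MAS and item 3 includes pain. All are assessed at one baseline and again at 2 weeks, 1 month and 3 months, counted from enrolment.

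**Analysis (Protocol, Statistical Analysis).** There are 25 patients in a cohort without a parallel group. Pre- and post-treatment values are compared with a paired test, and models of change take each patient's own baseline as the reference.

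**Timing (Protocol, Recruitment).** A patient may consent at the first treatment, or may take several weeks to decide.

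**Aim (Protocol, Purpose).** The study is to "evaluate if cryoneurolysis will be effective to control pain in patient with wrist and hand contracture".

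**Earlier readings.** Research Design says: "All measurements are a part of routine assessment for patients with severe spasticity and contracture". Criterion 5 makes response to a diagnostic nerve block (DNB) a condition of entry, so every participant has had a block visit. In Methods, after the description of the video made during the clinical assessment, the protocol adds: "All patients would have already had this done with their nerve blocks before the procedure".

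**The concern.** A patient measured at 3.8 cm qualifies and one measured at 4.2 cm does not, even if both have the same underlying distance. Patients admitted under a cut-off therefore include some whose reading that day happened to be low. When they are measured again, the group mean moves back toward its usual level without any treatment. The same holds for MAS, where the entry cut is at the severe end.

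If the qualifying reading is also the baseline, this movement is added to whatever the procedure does. With no control group, nothing in the data separates the two. Both the paired test and a mixed model that uses the baseline as its starting point absorb the shift as improvement. Objective 2 and Hypothesis 2, on spasticity, rest directly on such comparisons.

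Placebo response and natural change are inherent in a single-arm study. This component is not, because it can be removed without adding a control arm.

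**Working it through.** The protocol has no calculation to reproduce: 25 is a convenience sample, with no SD, reliability or effect size behind it.

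**Inputs from the protocol.** Cut-off 4 cm (Inclusion criteria, item 2); one baseline (Methods); n = 25 and a pre-post paired test (Statistical Analysis).

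**Assumptions.** Distance in the referred population is normal with mean 4 cm and SD 1.5 cm, so half of the patients fall below the cut-off. Test-retest correlation r is 0.6 to 0.95. The test is two-sided at 5%, so 2.5% in the direction of improvement. The treatment has no effect, and the qualifying value is the baseline.

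**Step 1, mean at entry.** With the cut at the mean, φ(0)/Φ(0) = 0.3989/0.5 = 0.798. Selected patients average 4 − 0.798 × 1.5 = 2.80 cm, which is 1.20 cm below the population mean.

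**Step 2, spurious gain.** Expected change with no effect = (1 − r) × 1.20 cm.

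**Step 3, SD of the change.** The variance of the selected baseline, in units of SD², is 1 − 2/π = 0.363. So SD of change = 1.5 × √[(1 − r)² × 0.363 + (1 − r²)].

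**Step 4, false-positive rate.** Standardised shift = gain ÷ (SD of change/√25). The rate is the chance that a t statistic with 24 df and this shift exceeds 2.064; simulation gives the last column.

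| r | Spurious gain (cm) | SD of change (cm) | Standardised shift | Falsely significant improvement |
|---|---|---|---|---|
| 0.6 | 0.48 | 1.25 | 1.91 | about 45% |
| 0.8 | 0.24 | 0.92 | 1.30 | 24% |
| 0.9 | 0.12 | 0.66 | 0.91 | 14% |
| 0.95 | 0.06 | 0.47 | 0.64 | 9% |

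Repeated simulations place the top figure between 43% and 46%.

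**Sensitivity to the share of referred patients below the cut-off** (SD units, two-sided rejection, r from 0.95 to 0.6):

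| Share below cut-off | Spurious shift | False rejection |
|---|---|---|
| 75% | 0.02 to 0.17 SD | 6% to 16% |
| 50% | 0.04 to 0.32 SD | 10% to 46% |
| 25% | 0.06 to 0.51 SD | 17% to 85% |

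**With a separate pre-treatment reading as baseline.** The expected change is 0.00 SD and two-sided rejection is 4.7% to 5.2% in every scenario.

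These figures are for distance. MAS is a graded scale, so the direction carries over but not the numbers.

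**The case against.** **The distance may be very repeatable.** It is measured at maximal passive extension, in a condition that the protocol defines by structural shortening. This stands. It makes the lower rows of the first table the more plausible ones for a fixed contracture. If most patients considered for cryoneurolysis already lie well below 4 cm, the shift is smaller still.

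**The protocol does not say that the qualifying reading is the baseline.** Correct. Candidacy rests on an earlier block response, and patients may take weeks to consent, so for many the two readings would differ. Consent at the first treatment is also allowed, however, and no sentence requires separate readings. The plan permits the bias; a reader might infer that it builds the bias in for everyone, and the text does not support that.

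**Pain is the first objective, so a reader might infer that the pain result is inflated to the same degree.** The protocol does not support this. Entry on pain depends on failure of usual treatment, which is a history rather than a score beyond a cut. Any figure for pain needs an invented threshold on the 0 to 10 scale as well as an assumed SD and correlation.

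**A reader might infer that pre-block scores exist for everyone.** The sentence about what was already done at the block refers to the video. Read with the statement that all measurements are routine, it makes earlier scores likely but not certain for every scale.

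**This is an exploratory pilot.** That softens the consequence. Significance tests of change and hypotheses of benefit are still planned.

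**Conclusion.** The point holds for distance and MAS. Both are entry thresholds and outcomes in an uncontrolled before-after study with one scheduled baseline, and the protocol does not keep the qualifying reading apart from it. Where they are the same reading, part of the apparent improvement is selection.

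The size is conditional on the assumed mean, SD, correlation and share below the cut-off, none of which the protocol gives. Under the main distance assumptions the gain is 0.06 to 0.48 cm, with about 9% to 45% falsely significant improvements against 2.5%. For pain the concern is one of principle, with no defensible number.

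It would go too far to treat the change from before the block to before the procedure as an untreated control. That interval contains a nerve block to which patients had to respond. If the earlier reading decides eligibility, the interval also contains the regression to the mean itself, while the later change does not.

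This is a removable weakness worth correcting, not a fatal flaw.

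**What to change.** 1. **Inclusion criteria:** state that distance and MAS eligibility is judged on an earlier routine clinic reading, the pre-block one where recorded, and note its date.
2. **Methods:** state that a fresh baseline is taken after eligibility is settled and before the procedure, and that only this baseline is the reference for change. Do not re-screen on it: a patient whose fresh reading crosses the threshold stays in, or selection returns.
3. **Reporting:** if the earlier values are shown, describe them as reflecting selection and possible carry-over from the block, not as an untreated comparison.
4. **Purpose and conclusions:** speak of change after cryoneurolysis rather than effectiveness, because placebo response, natural change and unblinded assessment remain.

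**Cost.** No extra staff or procedure is needed, since the measures are routine, but the use of earlier clinic values should be covered in the consent form. Earlier scores may be missing for some scales; the fresh baseline after eligibility is still needed then. The interval between readings will vary and should be recorded. The reported change may be slightly smaller.
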